Attachment 1. [name] Resume

Attachment 2. [name] CITI Certificate

Attachment 3. [name] Resume

Attachment 4. [name] CITI Certificate

Attachment 5. CW Approval of 2023-2024 SCC Follow-Up Pilot

Attachment 6. Survey Control Approval of 2023-2024 SCC Follow-Up Pilot

Attachment 7a. Screener survey

Attachment 7b. Pre-test survey

Attachment 7c. Post-test survey

Attachment 7d. 3Mo follow-up survey

Attachment 7e. 9Mo follow-up survey

Attachment 8. SCC and CHiPS acceptability survey

Attachment 9. Measurement x Timepoint Table

Attachment 10. Instructor Feedback Forms and Observer Logs

Attachment 11. Recruitment Materials (updated via Amendment 9)

Attachment 12. Instructor Resumes (names redacted)

Attachment 13. Instructor CITI Certificates (names redacted)

Attachment 14. Instructor COI Forms (names redacted)

Attachment 15. Research Coordinator CITI Certificate ([name])

Attachment 16. Research Coordinator Resume ([name])

Attachment 17. Research Coordinator COI Form ([name])

Endorsement by the Department Head or an individual with similar responsibility and authority. (Note: No individual listed on this protocol may sign this section.)

I approve this research to be conducted by personnel within my department. I will ensure that the research personnel in my department comply with all IRB laws, regulations, policies, decisions, conditions, and requirements.

[name], Colonel, USAF

Vice Superintendent

US Air Force Academy

(Signature waived for revision submission)

STATISTICAL ANALYSIS PLAN

Analysis Plan

Because of low follow-up survey participation rates among cadets who provided pretest survey data at the 3-month (13%) and 9-month (5%) assessments, only analyses of pre- to posttest data were conducted.¹ The outcomes examined and reported in this study were selected both because they were assessed at pre- and posttest and because they represent alcohol- and sexual assault-related factors that could reasonably change after participation in an integrated alcohol misuse and sexual assault prevention training (i.e., attitudes and knowledge). Study procedures and materials were reviewed by the USAFA Institutional Review Board and U.S. Army Medical Research and Development Command's Office of Human Research Oversight.

Descriptive statistics were computed for all variables to examine completeness and distribution. Group comparison tests (t-tests, chi-square tests, one-way analysis of variance) of participant characteristics at pretest were conducted to identify differences between conditions. To assess differences in change from pre- to posttest in outcomes by condition, we conducted mixed-effects multilevel models separately for each continuous outcome variable, with SCC + eCHECKUP TO GO set as the referent group. Independent variables included study condition (4-level: TAU, TAU + eCHECKUP TO GO, SCC, SCC+eCHECKUP TO GO), time, and time*condition. Covariates included cohort, race/ethnicity, and peer victimization. To examine moderation by sex, the models were replicated with the addition of interaction terms sex*time, condition*sex, and time*condition*sex. If the three-way interaction term was significant, models stratified by sex were computed. The same procedures were followed to determine whether condition effects were moderated by prior alcohol use. All analyses were computed in SAS version 9.4.

Measures: Sample Characteristics at Pretest

Sociodemographic information. All participants self-reported their age, sex, race/ethnicity, and sexual orientation.

Peer victimization. Past-12-month peer victimization was assessed with a three-item measure adapted from the Military Workplace Violence Study (Hourani et al., 2018). Participants self-reported how often one or more peers threatened their physical safety, put them through hazing activities, or harassed or bullied them (1: None of the time; 5: All of the time). Items were summed to create a continuous score.

Prior alcohol use. Participants self-reported their past-30-day alcohol use (as the number of drinks they typically had each day during a typical week during the month before arriving at USAFA) and were dichotomized based on whether they reported no alcohol use or any use.

Prior sexual assault victimization. Participants completed a 20-item measure derived from the Sexual Experiences Survey–Victimization (Testa et al., 2010) adapted based on cognitive testing with airmen (Goldstein & Scaglione et al., 2024). Items assessed whether participants had ever experienced unwanted sexual touching, intercourse, oral sex, anal sex, or other penetration. Participants were dichotomized based on whether they reported any or no prior sexual assault victimization.

¹ Analyses comparing 3- and 9-month survey responders and nonresponders identified systematic differences (in sex, prior alcohol use at pretest, and pretest readiness to change alcohol use behaviors) between the subsample of responders and total sample, indicating that presenting follow-up data could misrepresent the true program effects overall.

Prior sexual assault perpetration. Participants completed a 5-item measure adapted from the Sexual Experiences Survey–Perpetration (Johnson et al., 2017). Items presented combinations of behaviors that were and were not illegal according to the Uniform Code of Military Justice (e.g., “*Prior to arriving at USAFA, have you ever used a position of authority [such as being a coach, manager, or teacher] or taken advantage of someone in a compromising position [such as if you caught them breaking a rule] to have sex or do other types of sexual things with them when they indicated they didn’t want to?*”). This assessment strategy facilitated effective screening of prior perpetration behaviors for the purposes of this study without leading participants to endorse specific illegal behaviors. Participants were dichotomized based on whether they endorsed any or none of the items.

Measures: Alcohol–Related Outcomes (Pre- and Posttest)

Normative perceptions of peer alcohol use were assessed with a modified version of the quantity/frequency/peak questionnaire often used in peer-normative feedback research (Baer et al., 1991; Dimeff, 1999; Doumas et al., 2020). Participants were asked how many days in the week the average cadet of their same age and gender drinks (0–7 days) and how many drinks that average cadet consumes per day (0–6 or more); for analysis, these values were multiplied to compute the number of estimated drinks consumed per week.

Readiness to change alcohol use behaviors was assessed with one item, “Please indicate your readiness to change your drinking behavior.” Response options ranged from 0 “not at all ready” to 4 “very ready” (Reed et al., 2019).

Measures: Sexual Assault–Related Outcomes (Pre- and Posttest)

Knowledge of sexual assault was assessed using an 8-item scale adapted from previous research (Hanson & Gidycz, 1993, Kan et al., 2024). Participants were shown statements about sexual assault and indicated whether the statement was true or false; for example: “*Sexual assault always involves the use of physical force.*” Some statements were tailored to reflect participants’ knowledge of sexual assault specific to the Air Force or USAFA. Respondents received a score indicating the percentage of correct responses.

Knowledge of effective consent was assessed with 7 true/false items that included statements pertaining to sexual consent such as, “*If you are in a steady relationship, you still have to get consent for sex*” (Salazar et al., 2014, 2023). A score indicating the percentage of correct responses was computed.

Self-efficacy to resist unwanted sexual advances was assessed among a subset of participants across conditions (only those assigned to the primary sexual assault victimization prevention or sexual assault revictimization prevention categories). Using a 6-item scale, participants rated their degree of confidence (1 = not at all confident; 7 = very confident) in their ability to use certain strategies in high-risk situations, i.e., “*How confident are you that you could successfully resist someone’s pressuring if they were attempting to get you to consume alcohol, despite your wishes not to do so?*” (Hall, 1989; Kan et al., 2024; Marx et al., 2001). Individual items were summed to create a scale score ($\alpha_{\text{Pretest}} = 0.81$).

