misuse is associated with other negative effects on health and well-being, and (c) the Department of Defense is interested in cross-cutting prevention efforts that protect against multiple adverse outcomes such as alcohol misuse and sexual assault. As SCC is a sexual assault prevention program and accordingly addresses alcohol use to the extent that alcohol is related to sexual assault risk or experiences, there is benefit in determining whether additional alcohol misuse prevention content is associated with even stronger desirable effects on alcohol use-related outcomes. One candidate alcohol misuse prevention program is eCHECKUP TO GO, a brief (30-minute), personalized, web-based alcohol misuse prevention program developed by San Diego State University (SDSU). Based on an eCHECKUP TO GO program user's anonymous alcohol-related demographic information (e.g., biological factors influencing BAC) and experiences (e.g., alcohol use behavior prior to arriving at USAFA), personalized feedback is presented to modify cognitive risk factors for alcohol use and correct inaccurate norms perceptions that may increase risk for alcohol (mis)use. eCHECKUP TO GO has demonstrated feasibility, acceptability, and efficacy in previous studies of first-year undergraduate students (Doumas & Anderson, 2009; Doumas, Kane, Navarro, & Roman, 2011; Henry, Lange & Wilson, 2004; Hustad, Barnett, Borsari, & Jackson, in 2010; Lane & Schmidt, 2007; Steiner, Woodall & Yeagley, 2005; Wilson, Henry & Lange, 2005). In a different USAFA study (FAC20220024H HS-2022-0009), eCHECKUP TO GO was successfully beta-tested in a small sample of 22 volunteer cadets; findings suggested eCHECKUP could be acceptable and feasible to implement at USAFA. Taken together, there is merit to conducting a follow-up pilot study to investigate whether incorporating eCHECKUP TO GO yields additional prevention programming benefits above and beyond SCC or CHiPS alone.

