Summary of Changes from the 2022-2023 APY Pilot: This amended protocol seeks to build on findings, integrate minor recommended modifications from the 2022-2023 pilot study, and evaluate the potential additive positive effects of eCHECKUP TO GO on study outcomes. Specifically, we propose to collect data from a second cohort of the incoming 2023 BCT class (i.e., basic cadets during 2023 BCT throughout their year as fourth-degree cadets during the 2023-2024 APY). This will allow us to merge data collected from the 2022-2023 and 2023-2024 cohorts to better detect statistically significant effects on low-base-rate sexual assault outcomes, especially among smaller, higher-risk subgroups (e.g., among cadets who experienced sexual assault victimization prior to arriving at USAFA BCT). Feedback collected during the 2022-2023 pilot study informed the application of minor adjustments to the SCC program to enhance the program content and ensure training stays within bounds of protected SAPR BCT training time. In the planned 2023-2024 follow-up pilot study, we will also weave eCHECKUP TO GO into the SAPR prevention training. To achieve this, 3 out of 4 BCT squadrons assigned to receive SCC will also complete eCHECKUP TO GO during protected SAPR SCC time, and 3 out of 4 BCT squadrons assigned to receive CHiPS will also complete eCHECKUP TO GO during protected SAPR CHiPS time. To facilitate accurate condition assignment in study analyses (which can be challenging due to the anonymous nature of data collection), we are also proposing to include a new item assessing BCT squadron name in the pre-test and post-test assessments. This new item has already been approved by CW and A9, and it cannot be used to identify individual participants.

This study will have an important impact on the refinement and implementation of sexual assault prevention programming at USAFA and will help SAPR meet its goals of supporting and ensuring cadet well-being and

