We hypothesize that there will be some variability in program acceptability among cadets in the five different SCC training programs (healthy relationships/bystander intervention promotion; male revictimization prevention; male primary victimization prevention; female revictimization prevention; female primary victimization prevention). Based on our prior work at BMT and the 2021 USAFA BCT pilot study, we expect data will support SCC implementation feasibility and acceptability as indicated by few technological issues and high implementation fidelity among instructors. We also expect to observe meaningful increases from pre-test to post-test in knowledge of sexual assault and consent (across all participants), self-efficacy to resist unwanted sexual advances (among those who receive the primary victimization and revictimization prevention trainings), and bystander intentions (among those who receive the healthy relationships and perpetration prevention training). Based on 2022-2023 pilot study findings and the supporting theoretical and empirical evidence, we also expect all basics to show meaningful improvements in alcohol-related outcomes from pre- to post-training, but even stronger improvements among basics who receive eCHECKUP TO GO compared to basics who do not also complete eCHECKUP TO GO. This study will build on our prior work at BMT and the USAFA BCT pilot studies by examining whether anticipated effects are sustained over a 3- and 9-month follow-up period, which will help inform ideal timing of implementation and/or the need for booster training sometime following BCT. Follow-up assessments at 3 and 9 months will also allow for the assessment of changes in low-base-rate or occasional behaviors that may require more time to be observed.

Objective 1: Assess the feasibility and acceptability of implementing SCC with four-degree USAFA basic cadets in BCT (referred to as basics/basic cadets until they complete BCT).

Objective 2: Assess SCC program efficacy on proximal (knowledge, attitudes, beliefs, self-efficacy) and distal (protective behavior use, first-year sexual assault prevalence) outcomes compared to the Cadet Healthy Interpersonal Skills (CHiPS) TAU program across cadets' first year at USAFA.

Objective 3: Compare the efficacy of SCC alone to the combination of SCC plus eCHECKUP TO GO for alcohol use outcomes.

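### The SAP's referent coding answers Objective 3 but names no contrast for the protocol's wider eCHECKUP TO GO hypothesis, which is therefore addressed only within the SCC squadrons

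*Combined protocol and SAP*

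**What the plan says.** The SAP (Analysis Plan) describes mixed-effects models of pre-to-post change, one per continuous outcome. The terms are given as: "Independent variables included study condition (4-level: TAU, TAU + eCHECKUP TO GO, SCC, SCC+eCHECKUP TO GO), time, and time*condition". The coding is "with SCC + eCHECKUP TO GO set as the referent group", and the adjustment is: "Covariates included cohort, race/ethnicity, and peer victimization". The moderation models for sex and prior alcohol use reuse the same condition factor. The section names no other contrast.

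The protocol puts the eCHECKUP question in three ways:

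- Section 6 (Objectives), narrative: basics should improve on alcohol-related outcomes, with "even stronger improvements among basics who receive eCHECKUP TO GO compared to basics who do not also complete eCHECKUP TO GO". This is not limited to SCC.
- Section 5 (Background): the reason for the follow-up pilot is to learn whether "incorporating eCHECKUP TO GO yields additional prevention programming benefits above and beyond SCC or CHiPS alone".
- Section 6, Objective 3: "Compare the efficacy of SCC alone to the combination of SCC plus eCHECKUP TO GO for alcohol use outcomes". This is narrower.

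The 2023 allocation matches the wider question. In section 5, three of the four SCC squadrons receive eCHECKUP, and "3 out of 4 BCT squadrons assigned to receive CHiPS will also complete eCHECKUP TO GO during protected SAPR CHiPS time". Section 7 repeats this allocation.

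**The concern.** The 2023 design is a two-by-two layout: program (SCC or CHiPS) crossed with eCHECKUP (yes or no). The SAP treats its cells as four separate levels compared with one of them. Of the three time-by-condition coefficients this produces, only one changes eCHECKUP while holding program fixed, and it does so within SCC.

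CHiPS is the Academy's usual training, so whether eCHECKUP helps when added to it is a practical question that the study collected data to answer. If the plan is followed as written, that answer has no specified estimate. The hypothesis about all basics is then judged on the SCC side alone. If eCHECKUP works differently alongside CHiPS, the SCC coefficient does not estimate the effect across all basics.

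**Working it through.** The plan gives no sample size, power or error rate, so there is no figure to reproduce. The check is of the contrasts and their relative precision.

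**Which comparisons the coding gives.** Write SCC+e and TAU+e for the arms with eCHECKUP; TAU is CHiPS. Let b(TAU), b(TAU+e) and b(SCC) be the time-by-condition coefficients relative to SCC+e.

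- b(SCC) compares SCC with SCC+e. It isolates eCHECKUP, within SCC.
- b(TAU+e) compares TAU+e with SCC+e. It is a program comparison.
- b(TAU) compares TAU with SCC+e. It mixes program and eCHECKUP.

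The quantities not named are combinations of these:

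- TAU+e − TAU = b(TAU+e) − b(TAU)
- Averaged eCHECKUP effect = [(SCC+e − SCC) + (TAU+e − TAU)]/2 = [−b(SCC) + b(TAU+e) − b(TAU)]/2
- Difference between programs = (SCC+e − SCC) − (TAU+e − TAU) = −b(SCC) − b(TAU+e) + b(TAU)

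All three are estimable, but none is a single coefficient. A reader can combine published coefficients into a point estimate, but the standard error needs their covariances. A joint 3-df test of time by condition would not isolate eCHECKUP.

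**Precision: inputs.** 2023 squadrons are SCC+e 3, SCC 1, TAU+e 3, TAU 1 (protocol sections 5 and 7). For 2022 the documents say only that half the class received each program, without eCHECKUP; 4 SCC and 4 TAU squadrons are assumed. Merged counts are then 3, 5, 3 and 5. Squadrons are taken as independent, of equal size, with unit variance of mean change.

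**2023 alone**

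- SCC+e − SCC: variance 1/3 + 1/1 = 1.333, SE 1.155
- Averaged: (1.333 + 1.333)/4 = 0.667, SE 0.816
- SE ratio 0.816/1.155 = 0.707, or 29% smaller

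**Merged, change not adjusted for cohort** (the SAP lists cohort as a covariate but no cohort-by-time term)

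- SCC+e − SCC: 1/3 + 1/5 = 0.533, SE 0.730
- Averaged: (0.533 + 0.533)/4 = 0.267, SE 0.516
- SE ratio 0.707, again 29% smaller

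**Merged, change adjusted for cohort**

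- The cohort effect on change is estimated inside the SCC and TAU arms, 1 squadron against 4 in each. Its variance is (1 + 1/4)/2 = 0.625.
- All eCHECKUP squadrons are from 2023, against 1/5 of those without it. The correction is therefore 0.8 times the cohort effect, which adds 0.8² × 0.625 = 0.400 to each variance.
- SCC+e − SCC: 0.533 + 0.400 = 0.933, SE 0.966
- Averaged: 0.267 + 0.400 = 0.667, SE 0.816
- SE ratio 0.845, or 15% smaller

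**Difference between programs.** In 2023 the variance is 1.333 + 1.333 = 2.667, SE 1.63. In merged data it is 0.533 + 0.533 = 1.067, SE 1.03; the cohort correction cancels.

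**In terms of power.** Assume a common effect, two-sided 0.05 and a normal approximation. If the SCC-only contrast had 50% power, the averaged contrast would have 64% (merged, cohort-adjusted) to 79% (2023 alone, or merged without the adjustment). From 80%, it would have 91% to 98%. With so few squadrons these figures serve only to compare the two contrasts.

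**The case against.** The strongest reply is that the SAP does what the numbered objective asks. Objective 3 is SCC against SCC + eCHECKUP, and the chosen referent yields exactly that coefficient. Section 5 also closes by asking whether the integrated approach beats either part alone, which suits this referent. That stands, and a reader should not infer that the SAP ignores the eCHECKUP question. It answers the only numbered objective on it. What remains open is the wider expectation in section 6 and the stated aim in section 5.

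Second, all four conditions are in the model, so the missing quantities can be had on request. This also stands. The documents do not support the reading that the model is wrong or unable to give an answer for CHiPS, nor do they say that reporting will stop at the referent coefficients. They also promise nothing further, and a hypothesis without a specified estimate has no planned test.

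Third, the gain could be overstated. It is tempting to say that the averaged contrast is always worth a doubled sample. That holds for 2023 alone and for merged data without cohort adjustment of change. With that adjustment the variance ratio is 0.933/0.667 = 1.4, and CHiPS squadrons already inform the SCC contrast through the cohort term. Without it, 4 of the 5 assumed SCC-only squadrons are from 2022, so the merged SCC contrast is open to cohort differences in change.

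Fourth, added estimates bring some multiplicity, and the two supporting ones will be imprecise. In 2023, TAU+e against TAU is three squadrons against one.

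**Conclusion.** The point holds as a gap in what is specified. The SAP covers Objective 3 but names no contrast for the hypothesis about all basics or for benefit beyond CHiPS alone. The hypothesis is thus addressed only in the SCC squadrons, 4 of 8 in 2023.

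The averaged contrast would cut the standard error by 29% in 2023 alone, which rests on documented squadron counts. In merged data the cut is 15% to 29%, which rests on the assumed 2022 counts and depends on whether change is adjusted for cohort. All figures assume equal, independent squadrons, and the power figures also assume the same eCHECKUP effect in both programs. If the effects are a in SCC and c in CHiPS, the averaged contrast still estimates (a + c)/2, whereas the SCC contrast estimates a and misses that target by (a − c)/2.

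**What to change.** For each alcohol-related outcome, from the same fitted model:

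1. Keep SCC+e − SCC as the comparison for Objective 3.
2. Add [(SCC+e − SCC) + (TAU+e − TAU)]/2 on pre-to-post change, and name it as the test of the section 6 hypothesis about all basics.
3. Report TAU+e − TAU and (SCC+e − SCC) − (TAU+e − TAU) as supporting estimates with confidence intervals.
4. Because the SAP describes analyses already carried out, label items 2 and 3 as added after the reported analyses.
5. State whether change is adjusted for cohort, and give the 2022 squadron counts.

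The cost is three ESTIMATE statements in SAS per outcome and a few sentences in the SAP, with no new data. For the two alcohol-related outcomes listed, that is 3 × 2 = 6 further estimates, of which two are tests of a hypothesis already in the protocol. The difference contrast is weak (SE about 1.63 in 2023 and 1.03 merged, on the scale above), so an interval that includes zero must not be read as showing that eCHECKUP works equally well with both programs.

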(*Example: You are testing the effect of an educational software on learning, and you may benefit financially from the sale of this software.*)

If yes, please describe:

Click or tap here to enter text.

C. Do you have a professional interest in the outcome of this research? **No**

(*Example: The outcome of this research may be linked to future job offers from a co-sponsor of the research.*)

If yes, please describe:

Click or tap here to enter text.

D. Do you have a personal interest in the outcome of this research? **No**

(*Example: The outcome of this research may benefit the financial, professional, or personal circumstances of a family member or close friend.*)

If yes, please describe:

STUDY DESCRIPTION

5. Background

Provide an introduction, background information, and a review of the relevant literature. Answer the question: Why are you doing this study?

Sexual Assault Prevention and Response (SAPR) is a top priority of the Department of Defense and the United States Air Force (USAF). The USAF SAPR office (HAF/A1Z) has partnered with RTI International and colleagues on the development and evaluation of a tailored web-based (delivered via government issued laptop) sexual assault prevention training that can be integrated into standard classroom training to align with the objectives of the Air Force Sexual Assault Prevention Strategy (USAF, 2015). The Sexual Communication and Consent (SCC) training is an evidence-based program to promote healthy relationships and bystander intervention, while also reducing risk factors for sexual assault victimization, revictimization, and perpetration (Kan et al., 2020; Scaglione et al., 2020). Upon initial anonymous screening of gender and individual risk factors, participants are electronically routed to one of five tailored web-based prevention programs that aim to:

- Prevent/reduce perpetration and promote healthy relationships and effective bystander intervention,
- Reduce revictimization among males,
- Reduce revictimization among females,
- Prevent initial sexual assault victimization among males, and
- Prevent initial sexual assault victimization among females

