The baseline survey includes the screener instrument and the pre-test outcome measures (Attachments 7a and 7b, respectively). The baseline survey will be administered to the entire incoming class during the SAPR/CWIC BCT briefing, which occurs prior to the designated SAPR training time during which SCC, eCHECKUP TO GO (for the 2023-2024 cohort), and CHiPS will be delivered. The screener will assess demographic characteristics, prior sexual assault experiences, and other forms of trauma that have been empirically linked to increased risk for sexual assault. Upon receiving a study ID, basics will complete a screening instrument, which will determine their classification within one of five prevention categories: female primary victimization or revictimization prevention; male primary victimization or revictimization prevention; or healthy relationships & bystander intervention promotion. For basics assigned to receive SCC, the screener survey will also route the basic into the corresponding tailored web-based SCC programming. Immediately following the screener, cadets will complete the pre-test assessment, which assesses knowledge, attitudes, and behavioral intentions specific to their assigned program (skip patterns will be utilized to tailor measures to each participant's program assignment based on the screening items and to minimize respondent burden).

At the end of each of the 3 designated training sessions, basics assigned to receive SCC will be asked to complete a brief (less than 5 minutes) acceptability survey. Basics assigned to receive CHiPS will complete a similar acceptability survey after Day 3 only. (See Attachment 8 for copies of both acceptability instruments). After completing the Day 3 acceptability survey, all basics will complete the post-test survey to examine any immediate program-related changes in knowledge, attitudes, and behavioral intentions (Attachment 7c). All acceptability and post-test survey instruments are integrated into the overall 6-6.5-hour training time. All assessments are derived from validated, gold-standard measures published in the sexual assault and alcohol misuse prevention empirical literature. As stated earlier, the Measurement x Timepoint Table (Attachment 9) summarizes which constructs will be assessed during each timepoint throughout the study.

Follow-up Assessments

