measures, as they account for nested data (multiple assessments within person), which violate the assumption of independence associated with traditional regression methods. Further, latent growth models allow for modeling of non-linear trends, which are common when evaluating program effects, as initial improvements often plateau or drop back down over time. To the extent that we are powered to do so (likely only for male healthy relationships and female primary victimization programs), mediation models will test program effects on hypothesized mechanisms of change. For example, we hypothesize, based on prior work, that men exposed to the healthy relationships and bystander intervention program will exhibit increased intentions to intervene, which will in turn increase actual bystander intervention behavior.

Results will be analyzed both at the aggregate level and by program intervention group. Specifically, we will closely monitor screener data to ensure the automated screening algorithm functions properly and that cadets are receiving the content that is most appropriate. We will also compare rates of prior victimization and perpetration recorded via comprehensive assessment versus a brief assessment to determine whether a brief assessment could be sufficient for group assignment while also minimizing cadet burden. We will examine trends in responses across groups (e.g., higher levels of enjoyment or engagement among cadets in one training group over another) and visually examine trends in knowledge and attitude change to ensure effects are in the intended direction. This will also allow us to monitor for unexpected trends, including potential negative impacts on cadets.

8. Sample Size and Power Analysis

(Applies to “Full IRB Review” submissions) Describe how many participants you will need in total and for each subgroup in the study. Explain why your sample sizes are sufficient to achieve your study objectives. If appropriate, provide the details of a statistical power analysis including the assumptions underlying the analysis that helped you to arrive at your chosen sample size. Note: For minimal risk studies, the IRB asks for the minimum number of subjects that you require. You may exceed this minimum without amending your study. For greater than minimal risk studies, the IRB approves a maximum number of subjects. You may not exceed this number without an amendment approved by the IRB.

N/A, Exempt status

9. Subject Recruitment Methods

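### Self-efficacy is scored only in cadets routed to victimization tracks, so the sex moderation test on it, which has no term for track, cannot be attributed to sex alone.

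*Combined protocol and SAP*

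**What the plan says.** The SAP's section on sexual assault-related measures restricts self-efficacy, in every condition, to "only those assigned to the primary sexual assault victimization prevention or sexual assault revictimization prevention categories". The descriptions of the other outcomes state no such restriction.

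On how cadets reach those categories, protocol section 5 (Background) says: "Upon initial anonymous screening of gender and individual risk factors, participants are electronically routed to one of five tailored web-based prevention programs". Section 7 (BCT Assessments) lists the categories as "female primary victimization or revictimization prevention; male primary victimization or revictimization prevention; or healthy relationships & bystander intervention promotion". The screener comes before training and is given to the whole class. Skip patterns then fit the questions to the assigned category.

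The SAP's Analysis Plan fits its mixed models "separately for each continuous outcome variable", which takes in the summed self-efficacy score. For sex, "the models were replicated with the addition of interaction terms sex*time, condition*sex, and time*condition*sex". A significant three-way term leads to models stratified by sex. The covariates are peer victimization, cohort and race/ethnicity. Prevention category is not among them. Nor are prior victimization and prior perpetration, although both are measured at pretest.

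Section 7 (Data Analysis Plan) says that mediation models will be powered "likely only for male healthy relationships and female primary victimization programs". Its example concerns "men exposed to the healthy relationships and bystander intervention program".

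**The concern.** For an outcome asked of everyone, a sex moderation test compares the men in the class with the women in the class. For self-efficacy it compares the men and women whom a screener, using gender and risk factors, placed in a victimization track. The two scored groups may differ in the share receiving primary as against revictimization content, and in the risk history that put them there. If the training effect depends on either, the three-way term picks up that dependence and labels it sex.

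Two conclusions are at stake. A significant term would be presented as moderation by sex and followed by stratified models. A null term could be taken as a sign that the training works alike in men and women, when track mix may have masked a difference.

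**Working it through.** The plan has no figure to reproduce. Section 8 (Sample Size and Power Analysis) is marked as not applicable, and no counts by sex and track appear anywhere. Three checks are possible.

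**1. Do the documents imply that routing shares differ by sex?** Suppose men (number M) and women (number F) had the same chance q of the primary track and the same chance h of the healthy-relationships track. A larger female than male primary group needs qF > qM, so F > M. A larger male than female healthy-relationships group needs hM > hF, so M > F. Both cannot hold. If the Data Analysis Plan's remark on power is read as a remark on group size, it therefore implies different shares by sex, with many men in the category where self-efficacy is not scored. That reading is an inference. The passage speaks of power for mediation models and gives no headcounts.

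**2. How large could the track-mix component be?** All inputs here are assumed. Let p_m and p_w be the shares of scored men and women in the revictimization track, and let g be the effect in that track minus the effect in the primary track, in SD. With no true sex difference within a track:

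apparent sex difference = (p_m − p_w) × g

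- Example: effects of 0.40 and 0.20 SD, with shares of 60% in men and 25% in women: (0.60 − 0.25) × (0.40 − 0.20) = 0.35 × 0.20 = 0.07 SD.
- Low end of the range tried (g 0.1 to 0.3, p_w 20% to 40%, p_m 50% to 90%): (0.50 − 0.40) × 0.1 = 0.01 SD.
- High end: (0.90 − 0.20) × 0.3 = 0.21 SD.
- If p_m = p_w or g = 0, the result is 0.

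The same arithmetic can hide a difference. If the effect in men were truly 0.07 SD smaller within each track, a track-mix component of +0.07 would give 0.07 − 0.07 = 0.

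**3. How informative would a null term be?** If f is the male share of the scored subset, information for a sex interaction relative to an equal split is 4f(1 − f), and the standard error is multiplied by 1/√[4f(1 − f)]. The values of f are assumed.

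| Male share f | Relative information | SE multiplier |
|---|---|---|
| 5% | 0.19 | 2.29 |
| 10% | 0.36 | 1.67 |
| 20% | 0.64 | 1.25 |
| 30% | 0.84 | 1.09 |

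If men are a small minority of those scored, a null term says little even without any track-mix problem. Whether they are is not stated.

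**The case against.** The strongest reply is that routing rests on answers given before training and is applied in all conditions. The subset is therefore a baseline-defined subgroup, and routing does not bias the comparison of conditions within men or within women. The three-way term then validly describes whether the effect differs between the men and women who were routed to victimization tracks. The SAP claims only moderation by sex, and men and women differ in other characteristics for any outcome. All of this stands. What remains is that the SAP does not limit its interpretation to the routed subset, and that here, unlike for the other outcomes, entry to the scored group itself depends on gender.

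A second reply is that differential routing is not established. The screener attachment is not reproduced and the rule is not written out. Power for mediation also depends on behavioral outcomes, their base rates and follow-up response, not on group size alone. Male versions of both victimization tracks exist. This stands as well. A reader might infer that the men with self-efficacy data are a small, specially selected set and that the two sexes are not comparable samples. The documents make unequal routing plausible, but they do not support stating either as fact.

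A third reply is that adjusting for category is not a full cure. It removes track mix only. Selection into the subset may still differ by sex within a track. In the SCC conditions, men and women in the same kind of track also receive separate program versions. This stands, and it limits what the adjusted model can be said to show.

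**Conclusion.** The concern holds in a limited form. The documents state that self-efficacy is scored only in the two victimization categories, that gender and risk factors drive routing, and that the sex moderation test covers this outcome with no term for category. It follows that a significant or null three-way term on self-efficacy cannot be attributed to sex alone.

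The size is unknown. The range of 0.01 to 0.21 SD rests wholly on assumed shares and effects, and the component is zero when track shares or track effects are equal.

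A reader might go further and conclude that the self-efficacy results as a whole are biased, or that no reading of the sex test is supported. The documents do not support that. The within-sex condition contrast is not called into question, and a description limited to the routed subset remains legitimate. The point affects the interpretation of one moderation test on one outcome.

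**What to change.** For self-efficacy only:

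- Report the number of men and women per track and condition. That is 2 sexes × 2 tracks × 4 conditions = 16 cells.
- Alongside the model in the SAP, fit the sex moderation model with prevention category (primary or revictimization) and its time, condition and time-by-condition terms. With two time points and four conditions this adds 1 + 1 + 3 + 3 = 8 fixed effects.
- Call a difference moderation by sex only if it persists in that model.
- Limit the conclusion to cadets routed to victimization tracks. Note that track adjustment removes neither sex-specific selection into the subset nor the separate male and female program versions.
- If the male cells are too small to fit the added terms, present the sex result for this outcome as descriptive only.

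The category is already held for cadets in all conditions, so no new data are needed. The change also fits the protocol's stated intention to analyse results by program group as well as in aggregate. The cost is one extra model, one table of counts and a less precise sex interaction for this outcome.
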